Appendix 2.2. Endpoint Derivations

Appendix 2.2.1. Modified PODCI (Pediatric Parent):

For this study, a modified PODCI scale is being used where questions supporting only two PODCI subscale scores (ie, Transfer and Basic Mobility Core Scale and the Sports and Physical Functioning Core Scale) are being collected. The Pediatric Parent version will be completed by caregivers of participants.

Modified PODCI: Transfer and Basic Mobility Core Scale (Pediatric Parent):

The 11 items from the modified PODCI scale are mapped to the original PODCI scale using the below mapping strategy:

Modified	Original	
Q1	Q7	Put on his/her coat?
Q5	Q21	Climb one flight of stairs?
Q8	Q24	Walk one block?
Q9	Q25	Get on and off a bus?
Q12	Q28	Stand while washing his/her hands and face at a sink?
Q13	Q29	Sit in a regular chair without holding on?
Q14	Q30	Get on and off a toilet or chair?
Q15	Q31	Get in and out of bed?
Q16	Q33	Bend over from a standing position and pick up something off the floor?
Q17	Q34	How often does your child need help from another person for sitting and standing?

Modified	Original	
Q18	Q35	How often does your child use assistive devices (such as braces, crutches, or wheelchair) for sitting and standing?

The below algorithm is then applied to the mapped values to calculate the standardized score.

component	value	Result
Notes:	Any item rated "5" (Too young for this activity) is considered missing and is not added into the scale.	
	A minimum of 7 items must have valid answers to score this scale (including those marked "too young" as missing).	
	Q34 is RESCALED as follows: $Q34_{rescaled} = [(Q34 - 1) * 3/4] + 1$	Value ranging 1 to 4
	Q35 is RESCALED as follows: $Q35_{rescaled} = [(Q35 - 1) * 3/4] + 1$	Value ranging 1 to 4
Mean of Items:	(sum of items Q7, Q21, Q24, Q25, Q28, Q29, Q30, Q31, Q33, Q34Rescaled, Q35Rescaled) / (number of non-missing items)	Value ranging 1 to 4
Standardized Score:	$[(4 - \text{mean of items}) / 3] * 100$	Value ranging 0 to 100

Modified PODCI: Sports and Physical Functioning Core Scale (Pediatric Parent):

The 21 items from the modified PODCI scale are mapped to the original PODCI scale using the below mapping strategy:

Modified	Original	
Q2	Q18	Run short distances?
Q3	Q19	Bicycle or tricycle?
Q4	Q20	Climb three flights of stairs?
Q6	Q22	Walk more than a mile?
Q7	Q23	Walk three blocks?
Q10	Q26	How often does your child need help from another person for walking and climbing?
Q11	Q27	How often does your child use assistive devices (such as braces, crutches, or wheelchair) for walking and climbing?
Q19	Q36	Can your child participate in recreational outdoor activities with other children the same age?
Q20		Note: conditional on Q42 Too young?
Q21		Note: conditional on Q43 Activity not in season?
Q22	Q44	Can your child participate in pickup games or sports with other children the same age?
Q23		Note: conditional on Q50 Too young?
Q24		Note: conditional on Q51 Activity not in season?
Q25	Q52	Can your child participate in competitive level sports with other children the same age?
Q26		Note: conditional on Q58 Too young?
Q27		Note: conditional on Q59 Activity not in season?

Modified	Original	
Q28	Q60	How often in the last week did your child get together and do things with friends?
Q29		Note: conditional on Q65 Friends not around?
Q30	Q66	How often in the last week did your child participate in gym/recess?
Q31		Note: conditional on Q72 School not in session?
Q32		Note: conditional on Q73 Does not attend school?

The below algorithm is then applied to the mapped values to calculate the standardized score.

component	value	Result
Notes:	Any item rated "5" (Too young for this activity) is considered missing and is not added into the scale.	
	A minimum of 6 items must have valid answers to score this scale (including those marked "too young" as missing).	
	Q26 is RESCALED as follows: $Q26_{rescaled} = [(Q26 - 1) * 3/4] + 1$	Value ranging 1 to 4
	Q27 is RESCALED as follows: $Q27_{rescaled} = [(Q27 - 1) * 3/4] + 1$	Value ranging 1 to 4
	Q36 is RECODED to MISSING if (Q36 = 4 and EITHER [Q42 = "Y"] or [Q43 = "Y"])	Value ranging 1 to 4
	Q44 is RECODED to MISSING if (Q44 = 4 and EITHER [Q50 = "Y"] or [Q51 = "Y"])	Value ranging 1 to 4
	Q52 is RECODED to MISSING if (Q52 = 4 and EITHER [Q58 = "Y"] or [Q59 = "Y"])	Value ranging 1 to 4
	Q60 is RECODED and RESCALED as follows:	
	Step #1: Q60 is RECODED to MISSING if (Q60 = 3 and Q65 = "Y")	
	Step #2: If Q60 is not missing, $Q60_{rescaled} = [(Q60 - 1) * 3/2] + 1$	Value ranging 1 to 4
	Q66 is RECODED and RESCALED as follows:	
	Step #1: Q66 is RECODED to MISSING if (Q66 = 4)	
	Step #2: Q66 is RECODED to MISSING if (Q66 = 3 and EITHER [Q72 = "Y"] or [Q73 = "Y"])	
	Step #3: If Q66 is not missing, $Q66_{rescaled} = [(Q66 - 1) * 3/2] + 1$	Value ranging 1 to 4
Mean of Items:	(sum of items Q18, Q19, Q20, Q22, Q23, Q26rescaled, Q27rescaled, Q36, Q44, Q52, Q60rescaled, Q66rescaled) / (number of non-missing items)	Value ranging 1 to 4
Standardized Score:	$[(4 - \text{mean of items}) / 3] * 100$	Value ranging 0 to 100

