Velocity in meter/second is defined as 10 times the reciprocal of the time to complete the 10 meter run/walk test. For participants with a score of 0 on the 10 meter run/walk item (NSAA item 17), velocity will be set to 0. For participants with a missing score on the 10 meter run/walk item (NSAA item 17), velocity will be set to missing.

7. Change from Baseline at Week 52 in the rise from floor velocity.

Velocity is defined as the reciprocal of the time to rise from floor. For participants with a score of 0 on the rise from floor item (NSAA item 12), velocity will be set to 0. For participants with a missing score on the rise from floor item (NSAA item 12), velocity will be set to missing.

8. Change from Baseline at Week 52 in the Modified PODCI: Transfer and Basic Mobility Core Scale (Pediatric Parent)

The Modified PODCI: Transfer and Basic Mobility Core Scale (Pediatric Parent) consists of 11 items and assesses a participant's ability to walk, stand, and perform activities of daily living. The scale produces an independent, standardized score ranging from 0-100, with lower scores representing lower levels of function.

The Modified PODCI: Transfer and Basic Mobility Core Scale (Pediatric Parent) standardized score is calculated as described in [Appendix 2.2.1](#)

9. Change from baseline at Week 52 in the Modified PODCI: Sports and Physical Functioning Core Scale (Pediatric Parent).

The Modified PODCI: Sports and Physical Functioning Core Scale (Pediatric Parent) consists of 21 items and assesses a participant's ability to walk, stand, and perform

activities of daily living. The scale produces an independent, standardized score ranging from 0-100, with lower scores representing lower levels of function.

The Modified PODCI: Sports and Physical Functioning Core Scale (Pediatric Parent) standardized score is calculated as described in [Appendix 2.2.1](#).

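### Both PODCI scoring tables set every item rated 5 to missing, yet the rescaling of Q26, Q27, Q34 and Q35 works only if 5 is a scored, worst answer on those four items.

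*SAP*

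**What the plan says.** Section 3.2 lists change from baseline at Week 52 in two modified PODCI scales as secondary endpoints 8 and 9. Both run from 0 to 100, "with lower scores representing lower levels of function". Section 6.2.5 analyses each by MMRM, and Sections 5.4 and 6.2.5.2 add eCDF curves of within-patient change.

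Appendix 2.2.1 gives one scoring table per scale. Three elements matter here.

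- **Missing rule.** The first note in each table covers any item rated 5, glossed as "Too young for this activity) is considered missing and is not added into the scale". The next note sets the minimum number of answered items; for Transfer it begins "A minimum of 7 items must have valid answers to score this scale", and for Sports the minimum is 6.
- **Rescaling.** "Q34 is RESCALED as follows" and "Q35 is RESCALED as follows" in the Transfer table, and "Q26 is RESCALED as follows" and "Q27 is RESCALED as follows" in the Sports table, all lead to the formula (Q − 1) × 3/4 + 1 with a stated result of 1 to 4.
- **Score.** (4 − mean of the non-missing items) / 3 × 100, so a higher item value lowers the score.

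The four rescaled items ask about frequency, for example "How often does your child need help from another person for sitting and standing". The others concern use of assistive devices, or help with walking and climbing.

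**The concern.** The missing rule and the rescaling cannot both hold for these four items. The 3/4 factor maps five levels onto the 1-to-4 range of the other items, and its stated upper end needs a scored 5. The missing rule removes that answer. Since a higher item value means less function, the answer removed is the most impaired one.

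Nothing in the appendix settles which instruction prevails. The missing rule comes first and names no exception. Where an item needs its own missing condition (Q36, Q44, Q52, Q60, Q66), the Sports table writes one; Q26, Q27, Q34 and Q35 have no such line.

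At stake is whether two secondary endpoints, their baseline covariates and their eCDFs are derived correctly. A programmer who follows the note to the letter would treat a boy reported at the worst level of help or device use as if the question had not been answered.

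**Working it through.** **Inputs**, all from Appendix 2.2.1: rescaled value = (Q − 1) × 3/4 + 1; score = (4 − mean) / 3 × 100; 11 scored Transfer items, two of them rescaled this way (Q34, Q35); 12 scored Sports items, two of them rescaled this way (Q26, Q27). The average of the other items (2.0) is an illustrative assumption, and all other items are taken as answered.

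**Step 1: the stated range.** Raw answers 1, 2, 3, 4, 5 give 1.00, 1.75, 2.50, 3.25, 4.00. The plan's range of 1 to 4 is reproduced with 5 valid. With 5 missing the range is 1 to 3.25 and is not reproduced.

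**Step 2: score at one visit, other items averaging 2.0.**

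| Case | Mean, 5 valid | Score, 5 valid | Score, 5 missing | Error |
|---|---|---|---|---|
| Transfer, one item at 5 | (10×2 + 4)/11 = 2.182 | 60.6 | 66.7 | +6.1 |
| Transfer, both at 5 | (9×2 + 8)/11 = 2.364 | 54.5 | 66.7 | +12.1 |
| Sports, both at 5 | (10×2 + 8)/12 = 2.333 | 55.6 | 66.7 | +11.1 |

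In every literal case the remaining mean is 2.0, so the score is (4 − 2)/3 × 100 = 66.7.

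**Step 3: range of the single-visit error.** Dropping an item at the maximum of 4 can only lower the mean or leave it unchanged, so the score never falls. As the average of the items other than the rescaled pair runs from 4 down to 1:

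| Scale | One of the pair at 5, the other at 1 | Both at 5 |
|---|---|---|
| Transfer | +0.9 to +9.1 | 0 to +18.2 |
| Sports | +0.8 to +8.3 | 0 to +16.7 |

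The error is zero only when every remaining item is also at 4.

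**Step 4: change from baseline, which is the endpoint.** Take Transfer, with one item moving and the other ten fixed at an average of 2.0. The score with that item at raw 1, 2, 3, 4 is 69.7, 67.4, 65.2, 62.9. At raw 5 it is 60.6 if valid and 66.7 if missing.

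| Item, baseline → Week 52 | Change, 5 valid | Change, 5 missing |
|---|---|---|
| 1 → 5 | −9.1 | −3.0 |
| 2 → 5 | −6.8 | −0.8 |
| 3 → 5 | −4.5 | +1.5 |
| 4 → 5 | −2.3 | +3.8 |
| 5 → 4 | +2.3 | −3.8 |
| 5 → 1 | +9.1 | +3.0 |
| 5 → 5 | 0 | 0 |

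A 5 at Week 52 only pushes the change upward: decline is understated, or reversed when the item's earlier rescaled value was above the mean of the others (here 2.50 and 3.25 against 2.0). A 5 at baseline only does the opposite to improvement. A 5 at both visits cancels when the other items do not move.

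**The case against.** The best defence is the gloss in the note. It ties code 5 to the label for being too young, and the following note uses the same label. That label does not fit a question about how often help is needed. With the stated 1-to-4 range, this points to an intent to drop 5 only where it carries that meaning. A careful programmer may have done so, and the SAP does not show the program. This stands, and it makes the error conditional. It does not remove the conflict, because the text says any item and exempts none.

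Two further limits stand. The response options are not printed, so a five-level item with 5 as the worst answer is inferred from the formula and its range. The larger errors also need an unusual profile: the worst answer on both help and devices while the remaining items stay fairly good, in boys who are ambulatory and aged 4 to under 8.

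A reader might infer that the error always favours better function, or that any decline to 5 would appear as improvement. Step 4 shows otherwise: the upward shift holds for a score at one visit, change can err either way, and a fall from 1 or 2 to 5 still shows as a decline. A reader might also infer a biased treatment difference. The documents do not support that, since it would depend on how often 5 is given by arm and visit, which the SAP does not report.

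**Conclusion.** The contradiction is established from Appendix 2.2.1 alone: the missing rule as written is incompatible with the rescaling of Q26, Q27, Q34 and Q35. Read literally, it gives a wrong score whenever one of these items is 5 and the remaining items are not all at their worst. In the illustrations that is about 6 points with one Transfer item at 5, and 11 to 12 points with both items of a scale at 5, on a 0-to-100 scale. These figures assume literal programming, 5 as a valid worst answer, and other items averaging 2.0.

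Change from baseline may be too high or too low for an individual, and the size and direction of any effect on the group comparison are unknown. Neither PODCI scale is in the fixed testing sequence of Section 5.1, so the primary endpoint and the four alpha-controlled secondary endpoints are unaffected. The point should be corrected because a stated scoring rule would mis-score two secondary endpoints if followed; it does not threaten the trial's main conclusion.

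**What to change.** In both tables of Appendix 2.2.1, restrict the missing note to items whose code 5 carries the too-young label. Add that a 5 on Q34 and Q35 (Transfer) and on Q26 and Q27 (Sports) is a valid answer, enters the rescaling as 4, and counts towards the minimum number of answered items. Confirm this against the instrument's printed response options, which the SAP does not reproduce.

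Then check the derivation program with test records holding a 5 on each of the four items. The cost is one sentence per table and that check. If the program proves to have followed the note literally, the PODCI summaries, MMRM and eCDFs would have to be rerun; no new data are needed.

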Appendix 2.2.2. Categorical Classes for ECG of Potential Clinical Concern

Categories for QTcF

	Borderline	Prolonged	
QTcF (msec)	$450 \leq \text{max.} < 480$	$480 \leq \text{max.} < 500$	$\text{max.} \geq 500$

QTcF (msec) increase from baseline	30 ≤ max. <60	max. ≥60
--	---------------	----------

Categories for PR interval and QRS complex

PR interval (msec)	max. ≥300	
PR interval (msec) increase from baseline	Baseline >200 and max. ≥25% increase	Baseline ≤200 and max. ≥50% increase
QRS complex (msec)	max. ≥140	

Note: Additional summary for QRS complex and heart rate may be conducted

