2.3. Study Design

This is a Phase 3, global, multi-center, randomized, double-blind, placebo-controlled study to assess the safety and efficacy of fordadistrogene movaparvovec gene therapy in approximately 99 ambulatory male participants (in the FAS; see [Section 4](#)), ages ≥ 4 to < 8 years, with a genetic diagnosis of DMD who are on a stable daily regimen of glucocorticoids.

Eligible participants will be randomized into Cohort 1 or Cohort 2 in a 2:1 fashion and stratified by their age at Screening (< 6 or ≥ 6 years old). Study enrollment will be managed to ensure that no more than 55% of dosed participants are in either of the Screening age stratum. Enrollment will be assessed periodically, and if an imbalance is noted, enrollment of the overrepresented stratum may be paused until a more balanced distribution is achieved. In the context of this study, treatment will consist of two single intravenous infusions, one of fordadistrogene movaparvovec and one of placebo, with the timing and sequence as described below:

- Cohort 1 (approximately 66 participants): will receive a single dose of fordadistrogene movaparvovec on Day 1 (Visit 3) and a single dose of placebo at Day

DMB02-GSOP-RF02 4.0 Statistical Analysis Plan Template 01-Nov-2018

PFIZER CONFIDENTIAL

Page 14

TMF Doc ID: 98.03

390 (Visit 20). They will be followed for 5 years after the administration of the single dose of fordadistrogene movaparvovec. Total time on study will be approximately 5 years.

- Cohort 2 (approximately 33 participants): will receive a single dose of placebo on Day 1 (Visit 3) and a single dose of fordadistrogene movaparvovec at Day 390 (Visit 20), if they remain eligible. They will be followed for 5 years after the administration of the single dose of fordadistrogene movaparvovec. Total time on study will be approximately 6 years.

Figure 1. Study Schema

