3.5.3. Other Safety Endpoints

1. Complete physical examination and brief physical examination

If any finding on the physical examination is considered by the investigator to be ‘clinically significant’, the event is to be recorded as an AE, as appropriate.

2. Complete neurological examination and brief neurological examination

If any finding on the neurological examination is considered by the investigator to be ‘clinically significant’, the event is to be recorded as an AE, as appropriate.

3. Vital Signs

Vital sign parameters include body weight, height, body temperature, pulse rate, respiratory rate, O2 saturation (during 7-day hospitalization post IP administration), and supine blood pressure (systolic and diastolic).

4. Electrocardiogram (ECG)

A single 12-Lead ECG produces the following parameters, as assessed by a central reader: heart rate, PR, QT, corrected QT intervals (ie, QTcF corrected using Fridericia’s formula), and QRS complex.

5. Echocardiogram

The parameters from the echocardiogram include:

- LV Fractional Shortening: (%)
- LVEF: %
- Myocardial longitudinal strain -Global: %
- Myocardial circumferential strain – Global: %
- LV mass (g)
- LV end diastolic and end systolic volume (mL)
- Wall motion abnormalities (normal/ Hypokinetic/ Hyperkinetic/ Dyskinetic/ Akinetic/ Indeterminate)

- Location: LV Basal Anteroseptal, LV Mid Anteroseptal, LV Basal Inferolateral, LV Mid Inferolateral, LV Basal Inferoseptal, LV Mid Inferoseptal, LV Apical Septal, LV Basal Anterolateral, LV Mid Anterolateral, LV Apical Lateral, LV Basal Inferior, LV Mid Inferior, LV Apical Inferior, LV Basal Anterior, LV Mid Anterior, LV Apical Anterior.
- Wall thickness (mm)
 - Location: Interventricular Septum, LV Basal Inferolateral
- Pericardial effusion (present/absent)
 - Location: Pericardial Effusion Indicator: Present, Absent, Not Evaluable
- Pericardial effusion, thickness (mm)

6. Cardiac MRI

The parameters from the cardiac MRI include:

- LVEF (%)
- Myocardial strain parameters include:
 - Global longitudinal strain (%)
 - Global circumferential strain (%)
 - Global radial strain (%)

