6.7.4. Electrocardiograms

Changes from baseline (QT interval, heart rate, QTcF, PR interval, and QRS complex) in ECG parameters will be summarized descriptively for fordadistrogene movaparvovec and placebo by visit. Additionally, the number (%) of participants with ECG findings of potential clinical concern as defined in [Appendix 2.2.2](#) will be summarized for fordadistrogene movaparvovec and placebo.

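### QRS has one fixed class (140 msec or more) and no increase-from-baseline class, unlike PR and QTcF, so a large relative QRS widening below 140 msec is not counted

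*SAP*

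**What the plan says.** SAP Section 6.7.4 plans two ECG outputs. The first is a by-visit summary for each arm: "Changes from baseline (QT interval, heart rate, QTcF, PR interval, and QRS complex) in ECG parameters will be summarized descriptively". The second is "the number (%) of participants with ECG findings of potential clinical concern", with the classes taken from Appendix 2.2.2. Under Section 3.5.3 the intervals come from a single 12-lead ECG "as assessed by a central reader".

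Appendix 2.2.2 sets these classes:

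| Parameter | Absolute class | Increase-from-baseline class |
|---|---|---|
| QTcF | 450 to <480, 480 to <500, and ≥500 msec | 30 to <60 and ≥60 msec |
| PR | ≥300 msec | "Baseline >200 and max. ≥25% increase" or "Baseline ≤200 and max. ≥50% increase" |
| QRS | ≥140 msec | none |

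Below the classes stands "Note: Additional summary for QRS complex and heart rate may be conducted". It gives no threshold and no commitment. Section 2.3 describes the participants as male, "ages ≥ 4 to < 8 years, with a genetic diagnosis of DMD".

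**The concern.** Within one appendix, two of the three intervals are judged both against a fixed limit and against the boy's own baseline. QRS is judged against a fixed limit only. A fixed limit responds to relative widening only when the starting value is already close to it. The further below 140 msec a boy starts, the larger the proportional change he can have without being counted.

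At stake is how the categorical table reads. Section 2.2 lists ECG among the safety endpoints, to be judged on abnormal and clinically relevant changes, and the trial follows the heart closely with troponin, echocardiogram and cardiac MRI. An empty QRS row could be taken as evidence that no boy's conduction changed materially, when the criterion may have been out of reach for most of them.

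**Working it through.** The SAP gives no figure to reproduce here, so the check is threshold arithmetic.

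**Inputs from Appendix 2.2.2.** QRS class: maximum ≥140 msec. PR increase class for baselines of 200 msec or less: a rise of at least 50%.

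**Assumed input.** The SAP gives no baseline or normal QRS values. A baseline range of 60 to 100 msec is used for illustration only.

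**Step 1. Rise needed to reach the QRS class:** 140/baseline − 1. The last two columns show where a relative class would flag.

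| Assumed baseline QRS (msec) | Rise needed to reach 140 | Value after +50% | Value after +25% |
|---|---|---|---|
| 60 | +133% | 90 | 75 |
| 70 | +100% | 105 | 87.5 |
| 80 | +75% | 120 | 100 |
| 90 | +56% | 135 | 112.5 |
| 100 | +40% | 150 | 125 |

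**Step 2. Where a 50% widening escapes.** It stays below 140 when 1.5 × baseline < 140, that is, when baseline < 140/1.5 = 93.3 msec. A boy going from 80 to 120 msec is in no class. From 100 msec a 50% rise gives 150 and is counted by the existing class. The gap therefore covers the assumed range up to 93.3 msec and closes above it. This crossing point follows from the SAP's own cut-offs and does not depend on the assumed range.

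**Step 3. The PR rule for comparison.** For baselines of 200 msec or less, the PR flag falls at the smaller of 300 and 1.5 × baseline. With assumed PR baselines of 100, 120, 140 and 160 msec, that is 150, 180, 210 and 240 msec. The PR rule moves with the boy's own baseline; the QRS rule does not.

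**Step 4. Does the by-visit summary replace the count?** Section 2.3 plans about 66 boys in Cohort 1. If one of them widens by 40 msec, the arm mean moves by 40/66 = 0.6 msec. A maximum, if shown, would reveal that one value but not how many boys had such a change.

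**The case against.** The strongest reply is that little is lost. QRS changes are summarised by visit and arm whether or not a class is met. Appendix 2.1 (footnote to the ECG windows) also says that a qualitative abnormality flag feeds an incidence of abnormality. Troponin, echocardiogram, MRI and adverse event summaries cover cardiac injury by other routes. The amendment history in Appendix 6 records that the ECG classes were updated to align with the protocol, which is not shown and may explain the choice.

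Much of this stands. A reader might infer that marked conduction delay would be reported as no finding; the by-visit summary and the abnormality flag rule that out. What remains is that Section 6.7.4 specifies one participant count, "ECG findings of potential clinical concern" under Appendix 2.2.2. It names no table for the abnormality flag, and the SAP does not say what sets the flag. Alignment with the protocol explains where the classes came from, but it does not remove the difference between QRS and the other two intervals.

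Three further readings are tempting and not supported:

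- **That PR has the same weakness.** PR has a baseline-relative rule, and any rise of at least 50% from a baseline of 200 msec or less is counted. The class for baselines above 200 may be empty in these boys, but that does no harm because they fall under the other rule. Preferring 25% to 50% for PR is a matter of judgement.
- **That heart rate goes uncategorised.** Section 6.7.3 provides categorical tables of maximum increases and decreases in pulse rate, with further tables for the first 7 and first 30 days.
- **That these are adult cut-offs, or that the central reader holds age-specific limits that should replace them.** The SAP states neither. It shows only that the limits are fixed and not adjusted for age.

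**Conclusion.** The point holds for QRS alone. Appendix 2.2.2 gives QRS no increase-from-baseline class, and for baselines below 93.3 msec a widening of 50% or more that stays under 140 msec is missing from the participant-level table. The asymmetry and the 93.3 msec crossing point come directly from the SAP. How many boys start below that value depends on the assumed 60 to 100 msec range, which the SAP neither confirms nor contradicts. The loss is confined to one row of a descriptive safety table. No test, efficacy analysis or error rate is affected, so this is a cheap improvement and not a serious fault.

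**What to change.** In Appendix 2.2.2, beside the existing class of 140 msec or more, add a QRS increase-from-baseline class of at least 50%, and optionally one of at least 25%. Report new occurrences by arm in the Section 6.7.4 table. Delete QRS from the optional note, so that its summary is fixed in advance.

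The intervals are already read centrally, so the cost is a line of appendix wording and one or two table rows. SAP Section 2 allows the SAP to modify protocol plans and asks for a protocol amendment only for major changes to the primary endpoint or its analysis.

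The downside is a few more boys flagged in both arms, some through measurement noise. This weighs more on a 25% class: from an assumed baseline of 70 msec it needs only 0.25 × 70 = 17.5 msec, against 0.50 × 70 = 35 msec for the 50% class. That is why 50% is the main proposal and 25% the option. The placebo arm shows the background rate for either.
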